#### 7.4 Analysis of gestational age at maternal infection

We start with an analysis that assumes perfect test sensitivity and specificity. The gestational age at the onset of maternal infection is  $\pi_i(t)$ , t in weeks. Although the period of interest is between just before conception and delivery, ie the interval  $-2 \le t \le G_i$ ,  $\pi_i(t)$  is defined over a wider interval  $-2 - D \le t \le G_i + D$ , where D is the maximum duration of a test of persistence. This is because a first IgM+ test D weeks after delivery, or an IgM- test D+2 weeks before conception, both provide information about the probability of infection during pregnancy. Because there may be a finite probability that the maternal infection occurred before conception,  $\sum_{-2 \le t \le G_i} \pi_i(t)$  can take any value

between 0 and 1. Some special cases help clarify the concepts:

7.4.1 Onset of infection marked by symptoms. If a woman has symptoms in pregnancy starting at T then  $\pi_i(t) = 1$ , if t = T and  $\pi_i(t) = 0$ , if  $t \neq T$ .

7.4.2 Seroconversion alone. If the interval is defined by seroconversion during pregnancy, ie between a last lgG- at  $t_1$  and a first lgG+ at  $t_2$ , then in the absence of any other information,

$$\pi_i(t) = 1/(t_2 - t_1 + 1)$$
, if  $t_1 \le t \le t_2$ , else 0.

7.4.3 Surveillance data alone. Alternatively, suppose there are surveillance counts M(t) of suspected or confirmed cases (of ZIKV, DENV, or CHIKV) depending on the disease being studied [4], then the "a priori" distribution of when the infection might have occurred (given that it occurred in pregnancy) can be represented as a Dirichlet distribution:

$$\pi_i(t) = \alpha(t), \quad \alpha(t) \sim Dirichlet(M(t)), \quad -2 \le t \le G_i$$

7.4.4 PCR+ or IgM+, no surveillance data. If the specified interval is defined by a PCR+ or IgM+ test at time  $t_2$  and the earliest possible date of infection was  $t_1$  (which might be marked by an IgM- result, or  $t_1 = t_2 - D$ ) then, if the cumulative persistence distribution (the probability that persistence is d or less weeks) is  $F(d,\theta)$  with parameter(s)  $\theta$ , then (dropping the  $\theta$ ):

Author: [name] (UNIVBRIS)

20

$$\pi_i(t) = \frac{F(t_2 - t)}{\sum_{t_1 \le u \le t_2} F(u - t)}, \text{ if } -2 \le t \le t_2, \text{ else } 0$$

7.4.5 PCR+ or IgM+ with surveillance data. Now we assume the same test results, but surveillance data is available as well:

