$$\pi_i(t) = \frac{\alpha(t)F(t_2 - t)}{\sum_{t_1 \le u \le t_2} \alpha(u)F(u - t)}, \text{ if } t_1 \le t \le t_2, \text{ else } 0$$

7.4.6 If the infant is congenitally infected, and we have PCR+ or IgM+ with surveillance data as above, we need only consider scenarios in which the maternal infection occurs during pregnancy. The summation in the denominator is therefore over:  $Max(t_1, -2) \le u \le Min(t_2, G_i)$ 

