### 7.5 Using ZIKA-VT data to update prior information on test persistence

The previous section has shown how, given information on test persistence, the date of a positive PCR or IgM test informs the GA of maternal infection. In this section, we show how to estimate the distribution of test persistence from ZIKA-VT data, or, more usefully, how to update any prior information available.

Simplifying assumptions have been made for purposes of clarity and in order to keep the notation minimal: for example, that the date of onset of symptoms is taken to be the date of the onset of infection, and that tests are positive from that date. Adjustments can, and will, be made to accommodate these factors, but at this stage greater veracity would be at the expense of clarity.

 $F(d,\theta)$  is defined for d=1,2...D where D is the maximum possible duration of that marker. The data generated by ZIKA-VT and similar studies is *doubly interval censored*, because in most cases neither the onset of the marker response, nor the end of the marker response, is observed. Methods for analysis of doubly interval censored data have been published [5, 6] and have been applied to the timing of maternal infection in the context of congenital toxoplasmosis [7, 8]. A recent paper [9] includes a brief up-to-date review of the most commonly used methods.

ZIKV and the ZIKA-VT protocol have features that require extensions and modifications to existing methods. First, not only is incidence changing over time, but each individual woman is exposed to a different incidence which varies over the course of her pregnancy. Second, information on multiple markers in multiple types of samples will need to be processed simultaneously.

We begin with an analysis for a single marker, then we consider how to handle variables that might affect persistence, such as previous infection or the presence of symptoms, and finally the joint analysis of multiple markers.

[figure not shown]

Author: [name] (UNIVBRIS)

21

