#### 7.5.1 Estimating the persistence distribution of a single test

The objective here is to estimate the parameters  $\theta$  of the persistence distribution  $F(d,\theta)$  from data  $U_{Li}$ ,  $U_{Ri}$ ,  $W_{Li}$ ,  $W_{Ri}$  for every woman i, taking the following general form:

This represents a sequence of tests -++-, starting with a "last –ve" before the infection occurs at  $U_L$  and a first +ve after the infection at  $U_R$ . The onset of infection is within this interval. The date at which the test turns negative is between the last +ve at  $W_L$  and the first –ve at  $W_R$ . In practice, we may not observe a sequence -++- in a series of IgM or PCR tests in every woman. However, in combination with the occurrence of symptoms and the results of IgG tests, it will be possible to construct definite dates  $U_{Li}$ ,  $U_{Ri}$ ,  $W_{Li}$ ,  $W_{Ri}$  for every woman i who tests +ve on either IgM or PCR. For example, if symptoms occur at time T then  $U_{Li} = U_{Ri} = T$ ; if no final –ve test is observed, then  $W_{Ri} = W_{Li} + D$ ; if no initial –ve test is observed, then  $U_{Li} = U_{Ri} - D$ ; and so on. Note, also, that if a baby born to women i is confirmed to be congenitally infected, then this information requires that  $-2 \le t \le G$ ; in other words,  $U_{Li} \ge -2$  and  $U_{Ri} \le G_i$ .

If the data indicates that the GA of maternal infection is at t,  $U_{Li} \le t \le U_{Ri}$ , then the probability of the data given that t = T is:

$$\Pr(U_{L_i}, U_{R_i}, W_{L_i}, W_{R_i} \mid t = T, \theta) = \begin{cases} F(W_{R_i} - T - 1, \theta) - F(W_{L_i} - T - 1, \theta) & U_{L_i} \le T \le U_{R_i} \\ 0 & \text{otherwise} \end{cases}$$

Therefore, averaging over the distribution of maternal infection  $\pi_i(t)$ , the likelihood for the data is:

$$\Pr(U_{Li}, U_{Ri}, W_{Li}, W_{Ri} \mid \pi_i(t), \theta) = \sum_{i} \pi_i(t) (F(W_{Ri} - t - 1, \theta) - F(W_{Li} - t - 1, \theta)), U_{Li} \le t \le U_{Ri}$$

If the onset of infection at  $t_S$  is observed,  $U_{Li} = t_S = U_{Ri}$  and  $\pi_i(t_S) = 1$ , and the likelihood reduces to the standard likelihood for right censored or right interval censored data.

Author: [name] (UNIVBRIS)

22

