#### 7.5.2 Form of the distribution of persistence and impact of covariates

Analysis of the persistence distributions usually relies on standard two-parameter distributions, particularly Weibull, Gamma, and Log-logistic, and their 3-parameter generalisations. These parametric curves will be approximated by a piece-wise constant hazard  $\mu(d,\theta)$  during each time interval d, which gives us the cumulative distribution function (probability that the duration is  $\leq d$ ):

$$F(d,\theta) = 1 - \exp\left(-\sum_{u=1}^{\infty} \mu(u,\theta)\right)$$

In considering the appropriate form of these distributions, it is important to appreciate that the observed between-individual variation in duration of IgM reflects not only the stochastic uncertainty in how a single survival distribution is realized, but also between-individual variation in survival distributions, due to variation in the inoculum and variation in immune response. To better account for this, semi-parametric functions may also be fitted; for example, a random walk smoothing process applied to  $log \, \mu(d)$ 

The impact of covariates on persistence will be assessed, including: presence of symptoms, coinfection, and previous infection with the same or other arboviruses. Avidity tests will be used to determine whether an infection is primary or secondary.

A common strategy to study covariates is proportional hazards (PH), which introduces a single additional parameter  $\delta_X$  for each covariate X to the log hazard. Thus, in the presence of the covariate,  $\mu(d,\theta)$  is replaced by  $\mu(d,\theta)\,e^{\delta_X}$ . Otherwise, if PH is counter-indicated by the data, it can be relaxed and interactions between the covariate and time since infection can be introduced. The alternatives can be evaluated by residual analysis and global goodness of fit.

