#### 8.2 Analyses of properties of diagnostic tests

As noted earlier the ZIKA-VT and ZIKA-VID programs are inter-related and the analyses set out in *Section 7.5* will provide the definitive information on the persistence of IgM and other tests.

However, the population epidemiology data collected by ZIKA-VT also provides an opportunity for *supportive* analyses of test persistence, sensitivity and specificity. Results should be compared with the more formal evaluations undertaken as part of ZIKA-VID, which will comprise evidence from published literature as well as findings from *de novo* field work.

8.2.1 Average persistence of IgM. Given estimates of IgM prevalence (section 8.1.5) and incidence of primary infections based on seroconversion (section 8.1.4) or changes in cumulative incidence (section 8.1.6), estimates of the average persistence of IgM can be estimated by dividing IgM prevalence by IgM incidence.

We anticipate that IgM persistence may differ in women with previous ZIKV or DENV infections. If these women can be identified by avidity tests it will be possible to generate separate estimates of average IgM persistence for primary and secondary infections

8.2.2 Sensitivity and cross-reactivity of IgM and IgG tests. Estimates of sensitivity will be available for IgM and IgG tests in women with infections confirmed by PCR, and from cases where tests failed to detect infections in mothers of babies in whom congenital infection is demonstrated.

8.2.3 Specificity of IgM and IgG tests. Specificity of IgG tests can only be estimated in populations which are known to have not been exposed to the infection in question: this means that data collected in ZIKA-VT is not relevant to estimates of IgG specificity. However, IgM specificity can be studied by observing the relationship between the proportion of tests which are positive and the surveillance data over the previous 12 months. IgM persistence is believed to be about 12 weeks on average, so that an IgM+ occurring at a time when surveillance sources indicate there has been no virus circulating for over 4 or 5 months are highly likely to be false positives from a diagnostic point of view, whether due to persistent antibody, cross-reactions, or other factors; although it will be important to be able to rule out foreign travel before making these inferences. Data of this sort will be of great importance in defining the tails of the persistence distributions of IgM tests

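### Sections 7.4.4 and 7.4.5 date infection after a PCR+ or IgM+ result with F where the survival function is needed, and their denominator does not normalise

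*SAP*

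**What the plan says.** Section 7.4 sets out how the distribution of gestational age at maternal infection, pi_i(t), is built for each woman. Its premise is stated first: "We start with an analysis that assumes perfect test sensitivity and specificity". Section 7.5 adds the simplifying assumption that "tests are positive from that date", meaning from the date of onset.

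For a woman with a PCR+ or IgM+ at t2 and earliest possible onset t1, 7.4.4 introduces F as "the cumulative persistence distribution (the probability that persistence is d or less weeks"). Section 7.5.2 defines it the same way, as one minus the exponential of minus the summed hazard, "which gives us the cumulative distribution function (probability that the duration is" at most d). The likelihood in 7.5.1 uses the difference "F(W_{R_i} - T - 1, \theta) - F(W_{L_i} - T - 1, \theta"), which is non-negative only if F increases with duration.

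The weighting formula in 7.4.4, numerator then denominator, is "F(t_2 - t)}{\sum_{t_1 \le u \le t_2} F(u - t"), stated to apply for t from -2 to t2. In 7.4.5, with surveillance weights alpha, it is "\alpha(t)F(t_2 - t)}{\sum_{t_1 \le u \le t_2} \alpha(u)F(u - t"), stated for t from t1 to t2. Section 7.4.6 changes the range of summation when the infant is infected. Appendix A2.1 says that it expands the 7.4.5 formula for imperfect tests. It uses the sum of F(22-u) over weeks -2 to 20, times sensitivity, as the probability of a positive result given infection.

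**The concern.** A woman who tests positive at t2 and was infected at t must have a marker that lasted long enough to be present at t2. F(t2-t) is the probability of the opposite event. It is zero for onset in the week of the positive test and largest for the oldest candidate weeks.

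The denominator is a second, independent fault. A normalising constant must add up the weight of every candidate week u, so its argument should be t2-u. The printed argument is u-t.

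A third fault is that 7.4.4 gives a support starting at week -2 while its sum starts at t1. With t1 = t2-D, that start can fall on either side of -2.

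pi_i(t) enters the transmission function V(t) in 7.1, the severe-outcome function C(t) in 7.2, the averaging in the 7.5.1 likelihood, and the month or trimester probabilities that 7.7 carries into analyses like Tables 3 and 4. Gestational age at infection is the exposure named in objective 2.1. Section 7.8 allows for bespoke code, so the formulas may be programmed as they stand.

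**Working it through.** The SAP gives no numerical result here, so there is no figure to reproduce.

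**Inputs.** From the SAP: perfect tests (7.4); positive from onset (7.5); F is a cumulative distribution function (7.4.4, 7.5.2); Weibull is one of the named forms (7.5.2); a single IgM+ at week 20 with onset weeks -2 to 20 (the A2.1 example); and, from 8.2.3, "IgM persistence is believed to be about 12 weeks on average". Assumed, because the SAP gives no value: Weibull shape 1 to 3, flat incidence, and t1 = -2 unless stated.

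**Step 1, the correct weight.** With perfect tests and positivity from onset, P(positive at t2 | onset t) = P(duration exceeds t2-t) = 1 - F(t2-t). Call this S(t2-t). With a flat prior, pi_i(t) = S(t2-t) / sum over u of S(t2-u).

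**Step 2, the two weights side by side.** For shape 2 and mean 12, the Weibull scale is 12/Gamma(1.5) = 13.54 and F(d) = 1 - exp(-(d/13.54)^2). For IgM+ at week 20:

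| Onset week t | d = 20-t | F(d), as in the SAP numerator | S(d) |
|---|---|---|---|
| 20 | 0 | 0.00 | 1.00 |
| 19 | 1 | 0.005 | 0.995 |
| 10 | 10 | 0.42 | 0.58 |
| 0 | 20 | 0.89 | 0.11 |

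The two weights run in opposite directions.

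**Step 3, the printed formula taken literally** (F set to 0 at zero or negative arguments). At t = 19 the only non-zero denominator term is F(1), so the value is F(1)/F(1) = 1. At t = 20 it is 0/0. At t = -2, shape 2, it is 0.087. The values rise with t and, over -2 to 19, sum to 6.6 at shape 2 and to 5.1-7.8 over shapes 1 to 3. For a positive at week 30 the sum goes up to 8.5. Section 7.7 says that these probabilities cannot exceed one.

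**Step 4, denominator repaired but F kept**, i.e. F(t2-t) / sum over u of F(t2-u), against the correct S version. Ranges are over shape 1 to 3.

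| Test pattern | Mean onset week, F | Mean onset week, S | P(onset by week 13), F | P(onset by week 13), S |
|---|---|---|---|---|
| IgM+ week 20, t1 = -2 | 3.7-6.0 | 12.5-13.5 | 0.88-0.98 | 0.45-0.48 |
| IgM- week 8, IgM+ week 20 | 10.2-12.0 | 14.7-15.1 | 0.69-0.91 | 0.33-0.38 |

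At a given shape the shift runs from 12.5 - 6.0 = 6.5 weeks to 13.5 - 3.7 = 9.8 weeks in the first row. In the second it runs from 15.1 - 12.0 = 3.1 to 14.7 - 10.2 = 4.5 weeks.

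**Step 5, Appendix A2.1.** The sum of F(22-u) over u = -2 to 20 is 12.6 at shape 2 and 12.5-14.0 over shapes 1 to 3. It stands where a probability is needed. It also uses 22 as the origin although the test is at week 20.

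**Step 6, week convention.** In 7.5.1 a last positive at W_L implies a duration above W_L-T-1, so the matching survival weight is 1 - F(t2-t-1). Using it instead of 1 - F(t2-t) changes the correct mean little (13.0 to 12.7 at shape 2, 13.5 to 13.1 at shape 3, for IgM+ at week 20).

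**The case against.** A reader might infer that the SAP as printed dates infections far too early. The documents do not support that. The early shift in step 4 comes from an expression that is not in the SAP: it keeps the printed numerator and repairs the denominator. The printed denominator reverses the gradient. Rescaled to sum to 1, with the undefined week dropped (shape 2, t1 = -2), the literal formula gives mean onset week 13.0 for IgM+ at week 20, the same as the correct weight, with probability of onset by week 13 of 0.42 against 0.47. For IgM+ at week 30 it gives mean 21.2 against 22.7, and 0.17 against 0.08. This near-agreement is accidental and does not validate the formula, but it makes the early bias conditional.

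A reader might also infer that every gestational-age or trimester analysis is affected. That does not stand either. The basic tables of Section 6 use rules on test dates, symptom-dated women get a single week (7.4.1), and women dated by seroconversion alone get a uniform distribution (7.4.2). The 7.5.1 likelihood uses F correctly as a distribution function and inherits the fault only through pi_i(t).

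It can fairly be said that 7.4 offers these as special cases to clarify concepts, that the SAP describes parts of itself as generic, and that the week -2 to 20 window ignores the repeat testing planned in 5.1. The last point reduces the size, as the week 8 row shows, but does not remove it. The simplifications admitted in 7.5 concern the onset date and when tests turn positive; neither turns S into F. A2.1 builds on 7.4.5, so this is not a single slip of notation.

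**Conclusion.** The formulas in 7.4.4 and 7.4.5 are wrong as written. The weight uses the wrong function, the denominator does not normalise, and in 7.4.4 the support and the sum disagree. This follows from the SAP's own definition of F and needs no outside figure.

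The size depends on how the formulas would be coded. Literally, they give values summing to about 5 to 8 that are undefined at t2. With only the denominator repaired, onset is dated about 6.5 to 10 weeks too early for a lone IgM+ at week 20, and about 3 to 4.5 weeks too early with a negative at week 8. These sizes rest on the SAP's 12-week mean and on assumed Weibull shapes 1 to 3 and flat incidence; the first also assumes t1 = -2.

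The error matters for women whose pi_i(t) is taken from 7.4.4, 7.4.5 or A2.1, and through them for V(t), C(t), the 7.5.1 averaging and the trimester probabilities of 7.7. It should be corrected before any code is written.

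**What to change.** Define S(t2-t) as the probability that the marker is still positive at t2 given onset at t, and use one week convention throughout; 1 - F(t2-t-1) matches the 7.5.1 likelihood. Then:

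- 7.4.4: pi_i(t) = S(t2-t) / sum over t1 <= u <= t2 of S(t2-u), for t1 <= t <= t2, else 0.
- 7.4.5: pi_i(t) = alpha(t) S(t2-t) / sum over t1 <= u <= t2 of alpha(u) S(t2-u), for t1 <= t <= t2, else 0.
- 7.4.6: carry the same weights into the restricted range.
- A2.1: replace F(22-u) by S(20-u), and average it over the onset-week distribution instead of taking an unweighted sum.

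Numerator and denominator must be changed together, because repairing the denominator alone produces the early bias. A simple code check is that pi_i(t) sums to 1 over its full window under perfect tests and that, with flat incidence, it does not decrease towards t2. The cost is a text correction and a code check; no data collection changes.

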### 7.5 Using ZIKA-VT data to update prior information on test persistence

The previous section has shown how, given information on test persistence, the date of a positive PCR or IgM test informs the GA of maternal infection. In this section, we show how to estimate the distribution of test persistence from ZIKA-VT data, or, more usefully, how to update any prior information available.

Simplifying assumptions have been made for purposes of clarity and in order to keep the notation minimal: for example, that the date of onset of symptoms is taken to be the date of the onset of infection, and that tests are positive from that date. Adjustments can, and will, be made to accommodate these factors, but at this stage greater veracity would be at the expense of clarity.

 $F(d,\theta)$  is defined for d=1,2...D where D is the maximum possible duration of that marker. The data generated by ZIKA-VT and similar studies is *doubly interval censored*, because in most cases neither the onset of the marker response, nor the end of the marker response, is observed. Methods for analysis of doubly interval censored data have been published [5, 6] and have been applied to the timing of maternal infection in the context of congenital toxoplasmosis [7, 8]. A recent paper [9] includes a brief up-to-date review of the most commonly used methods.

ZIKV and the ZIKA-VT protocol have features that require extensions and modifications to existing methods. First, not only is incidence changing over time, but each individual woman is exposed to a different incidence which varies over the course of her pregnancy. Second, information on multiple markers in multiple types of samples will need to be processed simultaneously.

We begin with an analysis for a single marker, then we consider how to handle variables that might affect persistence, such as previous infection or the presence of symptoms, and finally the joint analysis of multiple markers.

[figure not shown]

Author: [name] (UNIVBRIS)

21

#### 7.5.1 Estimating the persistence distribution of a single test

The objective here is to estimate the parameters  $\theta$  of the persistence distribution  $F(d,\theta)$  from data  $U_{Li}$ ,  $U_{Ri}$ ,  $W_{Li}$ ,  $W_{Ri}$  for every woman i, taking the following general form:

This represents a sequence of tests -++-, starting with a "last –ve" before the infection occurs at  $U_L$  and a first +ve after the infection at  $U_R$ . The onset of infection is within this interval. The date at which the test turns negative is between the last +ve at  $W_L$  and the first –ve at  $W_R$ . In practice, we may not observe a sequence -++- in a series of IgM or PCR tests in every woman. However, in combination with the occurrence of symptoms and the results of IgG tests, it will be possible to construct definite dates  $U_{Li}$ ,  $U_{Ri}$ ,  $W_{Li}$ ,  $W_{Ri}$  for every woman i who tests +ve on either IgM or PCR. For example, if symptoms occur at time T then  $U_{Li} = U_{Ri} = T$ ; if no final –ve test is observed, then  $W_{Ri} = W_{Li} + D$ ; if no initial –ve test is observed, then  $U_{Li} = U_{Ri} - D$ ; and so on. Note, also, that if a baby born to women i is confirmed to be congenitally infected, then this information requires that  $-2 \le t \le G$ ; in other words,  $U_{Li} \ge -2$  and  $U_{Ri} \le G_i$ .

If the data indicates that the GA of maternal infection is at t,  $U_{Li} \le t \le U_{Ri}$ , then the probability of the data given that t = T is:

$$\Pr(U_{L_i}, U_{R_i}, W_{L_i}, W_{R_i} \mid t = T, \theta) = \begin{cases} F(W_{R_i} - T - 1, \theta) - F(W_{L_i} - T - 1, \theta) & U_{L_i} \le T \le U_{R_i} \\ 0 & \text{otherwise} \end{cases}$$

Therefore, averaging over the distribution of maternal infection  $\pi_i(t)$ , the likelihood for the data is:

$$\Pr(U_{Li}, U_{Ri}, W_{Li}, W_{Ri} \mid \pi_i(t), \theta) = \sum_{i} \pi_i(t) (F(W_{Ri} - t - 1, \theta) - F(W_{Li} - t - 1, \theta)), U_{Li} \le t \le U_{Ri}$$

If the onset of infection at  $t_S$  is observed,  $U_{Li} = t_S = U_{Ri}$  and  $\pi_i(t_S) = 1$ , and the likelihood reduces to the standard likelihood for right censored or right interval censored data.

Author: [name] (UNIVBRIS)

22

In a Bayesian framework, we may incorporate already published data on the parameters  $\theta$ . For example, a persistence distribution has been published for a ZIKV RT-PCR, characterized as a Weibull distribution [10]. Either informative priors for  $\theta$  based on the published material can be entered, or published results on  $F(d,\theta)$  itself and its confidence intervals can be built in, in a form of multiple parameter evidence synthesis [11]; see Guyot [12] for a similar example.

We will check for conflict between the ZIKA-VT data and any prior information by testing the impact of removing the prior information and the use of goodness of fit statistics  $\bar{D}$  and DIC [13].

Appendix 3 details the publications which will be used to provide prior information on persistence parameters that will be incorporated in the statistical analysis. This table will be routinely updated.

